## Project Details

### I. Project Introduction

**I.1** *Project to be reviewed by:*  
IRB-01

**I.2** *Project Title:*  
Evaluating racial and ethnic differences in micropore closure using optical coherence tomography

**I.3** *Short Title (optional):*  
Visualizing micropore closure with OCT

**I.4** *Provide a short summary of the purpose and procedures of the study proposed in this IRB application.*

- ***DO NOT include information on studies not proposed in this application.***
- ***Use LAY terminology only. This must be easily understandable by IRB community members and nonscientists.***
- ***DO NOT cut and paste technical abstracts from funding applications that may not be understood by a general audience.***

The purpose of this study is to use an innovative, noninvasive imaging technique called optical coherence tomography (OCT) to visualize micropore closure in racial/ethnic skin following micropatch application. Healthy and consenting adult volunteers (18-45 years old) will be enrolled. Subjects will be asked to self-identify their race and ethnicity according to the following groups: Black, Asian, Latinx, White, Indigenous, or Bi-/multi-racial/other. All subjects, regardless of self-identified race/ethnicity, will receive the same micropatch treatment and measurements. The micropatches are patches containing a small array of microneedles on an adhesive patch backing; the whole micropatch fits on the tip of a thumb. The micropatches will be applied to the upper arm, forearm, and the palm. At each of these locations, 3 sites will be identified. One site will receive micropatch application followed by occlusion with a small patch (note: this is just a band-aid like patch, not a micropatch). The other 2 sites will be controls: one site will be treated with a micropatch but will not be covered afterwards, and the other site will be an occlusion control site (covered with an occlusive patch but no micropatch application). Noninvasive measurements will be made at baseline to determine

differences in hydration, skin water loss, electrical resistance (impedance), and color between subject groups. OCT scans will be made on the skin to noninvasively visualize the skin structure, allowing calculations of epidermal thickness and microvasculature density. After the micropatch is applied to one site at each of the 3 body locations, the water loss, impedance, and OCT measurements will be repeated. The micropatches are only applied on the first study day.

Impedance and OCT measurements will be repeated at 24 hrs and 48 hrs. The impedance measurements will allow us to mathematically calculate the time it takes for the skin barrier to restore after the micropatch application, and the OCT images will give us an innovative and complementary method for visually confirming the impedance calculations.

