#### **I.5**

##### ***Specify your research question(s), study aims or hypotheses (do not indicate "see protocol")***

This study aims to visualize micropores and measure micropore closure rates following micropatch application at 3 anatomical sites in subjects from different racial/ethnic groups. Another study aim is to quantify differences in skin structure and blood flow using OCT imaging. We hypothesize that OCT images of micropores in the skin will provide a complementary approach to calculating micropore lifetime, when combined with impedance calculations.

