OCT is a noninvasive and nondestructive technique that is already recognized as a powerful medical imaging technique

in the field of ophthalmology, in which it is used for imaging the retina. It is a real time, in-vivo technique that has also been used for skin imaging. The instrument uses an echo technique for image collection that is similar in concept to ultrasound, with the exceptions that OCT uses light waves (instead of sound waves) and provides better resolution. OCT allows for noninvasive observation of the skin in a vertical plane up to a depth of ~1 mm, capturing two and three-dimensional images [6]. This allows for visualization of multiple skin structures such as the epidermis, dermis, epidermal junction, and hair follicles. Dynamic OCT allows for the visualization of the microvasculature, along with the skin structures. Previous studies have successfully utilized OCT to image polymeric microneedles in the skin [7-8]. However, OCT has not been used to visualize the micropores formed from metal microneedles, which is the primary focus of the work in our lab group. To date, there are also no studies using OCT to study the microvasculature differences among different racial/ethnic skin types.

In our research program we recently demonstrated that epidermal barrier restoration is slower after microneedle application in darker skin types [9]. We also demonstrated that the use of tristimulus colorimetry as a quantitative measurement of skin color is a better indicator of skin variability than race self-reported by subjects. Using OCT to visualize the skin structures will provide a visual, complementary confirmation of these findings that will augment the impedance calculations that we use as a surrogate measure to determine how long the micropores remain open.

In the current study we will use dynamic OCT and other noninvasive measurements of epidermal properties to comprehensively examine differences in skin properties and micropore closure timeframes after microneedle application in a population of healthy human subjects with racial/ethnic skin.

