- Transepidermal water loss (TEWL) will be measured by resting a probe gently against the skin. This measurement will take 1-3 minutes at each site. (TEWL will only be measured on Day 0)
- Electrical resistance (impedance) will be measured with an impedance meter by applying gel electrodes to each site and a reference electrode at a nearby site. The measurement will be repeated 3 times at each site, and will take less than 2 minutes total at each site.
- Skin color and redness will be measured by placing a colorimetry probe gently against each site. This measurement will take less than 30 seconds at each site.
- Dynamic-OCT will be used to obtain an image of the skin by holding a probe lightly on the skin. This measurement will take about 30 seconds at each site. Microvasculature density, epidermis thickness, and epidermal junction depth can be measured using a single scan.

Following baseline measurements on Day 0, micropatches (an adhesive microneedle patch) will be applied to two of the three identified sites at each anatomical location. The sites will first be cleansed with an alcohol swab. A sterilized micropatch

containing 50 tiny projections, each 800 um in length, will be placed perpendicular to the skin, and the researcher will apply gentle pressure to the back of the patch for 15 seconds. A new micropatch will be used for each site, and the micropatches will be discarded immediately after use. Micropatch application will only occur on Day 0. Immediately after treating a site with a micropatch, TEWL, OCT and impedance measurements will be repeated. One of the micropatch sites at each location will be covered with a sterile occlusive covering following micropatch application; this will be secured to the skin using medical tape such as Tegaderm or Bioclusive tape. The second micropatch application site at each location will not be covered. The third site at each location will not receive micropatch application, but will simply be covered with an occlusive covering. This serves as a control for the effect of occlusion alone on normal skin. Day 0 procedures will require 3 - 3.5 hours in total.

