Subjects will be asked to return to the College of Pharmacy every 24 hours for the next 2 days. On each day the occlusive coverings will be removed and the OCT and impedance measurements will be repeated at all sites. Fresh occlusive coverings will be applied after measurements have been completed. Procedures on days 1 and 2 will require approximately 2 – 2.5 hrs.

On Day 2 (the final day), the occlusive coverings will be removed and not replaced. Within 3-6 days after the Day 2 visit (or the last completed visit if a participant decides to drop out early) a study team member will contact the subject via phone or email to determine if the subject is experiencing any redness or irritation at any of the measurement sites. No long-term follow-up will be necessary. The overall time commitment for this study is 7 - 10 hours in one week, across 3 – 4 study days if consent is obtained on a different day than the study start day.

To summarize, the 9 sites will receive the following measurements and treatments:

Palm: sites 1 – 3

Site 1: Micropatch application + occlusive covering

Site 2: Micropatch application, no occlusive covering

Site 3: Occlusive covering, no micropatch application

Forearm: sites 4 – 6

Site 4: Micropatch application + occlusive covering

Site 5: Micropatch application, no occlusive covering

Site 6: Occlusive covering, no micropatch application

Upper arm: sites 7 – 9

Site 7: Micropatch application + occlusive covering

Site 8: Micropatch application, no occlusive covering

Site 9: Occlusive covering, no micropatch application

Measurements of TEWL, Dynamic-OCT, colorimetry, and impedance will be made at baseline (Day 0) for all sites. TEWL, Dynamic-OCT, and impedance measurements will be repeated immediately after micropatch application. Dynamic-OCT and impedance measurements will be measured at all sites on days 1 and 2.

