## **XI. Data Analysis**

**XI.1** *Describe the analysis methods you will use, including, if applicable, the variables you will analyze*  
Paired t-tests will be performed to compare impedance and TEWL measurements pre- and post-micropatch treatment at each site. Influence of skin color and self-reported ethnicity/race on measured parameters will be compared using one-way ANOVA. Micropore closure kinetics will be calculated by modeling the data and calculating a micropore closure half-life. Epidermal thickness, skin roughness, and microvasculature density will be calculated by the OCT software and compared between groups using one-way ANOVA. For all analyses,  $p < 0.05$  will be considered statistically significant. GraphPad Prism Software (GraphPad Software, San Diego, CA) or Microsoft Excel will be used for statistical analyses.

**XI.2** *Provide the rationale or power analysis to support the number of subjects proposed to complete this study.*  
This is a pilot study that does not require a power analysis because data regarding the variability in parameters measured via OCT in racial/ethnic groups is not available. We are targeting 20 subjects per group because this is a reasonable number of subjects for a pilot.

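### Visual OCT reading of micropores is meant to confirm impedance and the earlier skin-color finding, but the plan does not mask it, so the confirmation would not be independent evidence

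*Combined protocol and SAP*

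**What the plan says.** OCT has two confirming roles. In I.4, "the OCT images will give us an innovative and complementary method for visually confirming the impedance calculations". In I.6, the team reports that "we recently demonstrated that epidermal barrier restoration is slower after microneedle application in darker skin types" and continues: "Using OCT to visualize the skin structures will provide a visual, complementary confirmation of these findings". The hypothesis in I.5 is worded more mildly: "OCT images of micropores in the skin will provide a complementary approach to calculating micropore lifetime, when combined with impedance calculations".

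VII.E.6 takes both measurements at the same visits. On Days 1 and 2, "the occlusive coverings will be removed and the OCT and impedance measurements will be repeated at all sites". Its closing list fixes the numbering: sites 1, 4 and 7 get a micropatch and a cover, sites 2, 5 and 8 a micropatch without a cover, and sites 3, 6 and 9 a cover only.

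For analysis, XI.1 states: "Epidermal thickness, skin roughness, and microvasculature density will be calculated by the OCT software and compared between groups using one-way ANOVA". It also plans a closure half-life from a model, and I.4 ties closure time to impedance.

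The application does not mention masking. It names no OCT reader, gives no rule for calling a pore open or closed, and sets no order between reading the scans and seeing the impedance data. X.1 puts subject numbers on study materials as a privacy measure.

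**The concern.** Whether a micropore is still visible on a scan is a judgement. I.6 says that OCT has not yet been used on pores made by metal microneedles, and the plan cites no reading standard, so some unclear scans are to be expected. When the expected answer is written down beforehand and the reading is not masked, unclear scans can drift toward that answer.

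At stake is the independence of the imaging evidence. The study title and first aim rest on seeing pores close, and the result would be cited as imaging support for a difference that the team has already reported from impedance. If the reader could see impedance or group while judging the scan, agreement between the two methods would add little.

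**Working it through.** The plan gives no figure for this point, so there is none to reproduce. The check is a scan count, then a comparison of what is promised with what is protected.

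**1. Scans per subject (VII.E.6)**
- Baseline: 9 sites = 9
- Immediately after application: 3 locations × 2 micropatch sites = 6
- Days 1 and 2: 9 sites × 2 = 18
- Total: 9 + 6 + 18 = 33

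**2. Scans that could show micropores**
- Micropatch sites after application: 6 sites × 3 time points = 18
- The rest: 9 baseline + 3 cover-only sites × 2 days = 15. No micropatch had been applied to the skin in these scans.
- Check: 18 + 15 = 33. For the 100 subjects in VI.1, 18 × 100 = 1,800 if all complete.

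**3. What could reach the reader**

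| Information | Where it arises | Kept from the reader by the plan? |
|---|---|---|
| Impedance | Same visits as OCT (VII.E.6) | Not stated |
| Self-identified group | Screening (VII.D.20, VII.D.26) | Not stated |
| Site condition | Fixed site numbers (VII.E.6) | Not stated; a site number gives it away |
| Visit | Day of the scan | Not stated |

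The subject number in X.1 removes direct identifiers. It does not hide site or day, and nothing says that it separates a scan from group or impedance.

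**4. Which outputs depend on a visual judgement**
- Epidermal thickness, roughness and microvasculature density: calculated by software (XI.1), so outside this point.
- Closure half-life: modelled. XI.1 does not name the input, but I.4 ties it to impedance. Outside this point.
- Visual confirmation of closure: promised in I.4 and I.6, with no matching variable, rule or comparison in XI.1. This is where the point applies.

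**5. Scale, under an assumption that is not in the documents**

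Suppose the team compared a continuous, visually judged closure measure between two groups of 20 (XI.2) with no true difference, and expectation shifted one group's mean by *b* standard deviations. The noncentrality of the two-sided 5% t-test (38 degrees of freedom) is *b*√(20/2).

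| *b* | Noncentrality | Chance of p < 0.05 |
|---|---|---|
| 0 | 0 | 5% |
| 0.25 | 0.79 | 12% |
| 0.5 | 1.58 | 34% |
| 0.75 | 2.37 | 64% |

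XI.1 lists no such test and *b* is unknown. The table shows only that a modest shift would matter at this sample size. It is not an estimate for this study.

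**The case against.** The strongest reply is that the plan analyses nothing that a reader's expectation could move. The three OCT variables compared between groups come from software, and closure time comes from impedance. This stands. A reader might infer that the planned group comparisons are biased by whoever reads the images, and XI.1 does not support that. Choices made while scanning, such as probe placement, are not described, and coding the images afterwards would not address them.

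Second, the application is silent on who reads the scans and what that person knows. A reader might infer that the team reads them knowing group and impedance. The documents do not say so. The supportable statement is that the plan does not prevent it. The attached data collection sheets (VII.E.4) are not reproduced and could hold a reading rule. However, VII.B.11 says that no separate protocol exists, and neither VII.E.6 nor XI.1 refers to such a rule.

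Third, I.4 must be written in lay terms, I.5 speaks only of a complementary approach, and this is a pilot. That softens the wording, but I.6 repeats the claim of confirmation outside the lay summary. Pilot status explains the missing power analysis in XI.2. It does not explain leaving out a safeguard that costs little.

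The absence of a planned agreement analysis does not weaken the point. Without one, confirmation would rest on impression.

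**Conclusion.** The point holds for the visual reading of micropores only. As written, the plan promises imaging confirmation of a result stated in advance and does not mask the reading that would supply it. Such confirmation could not be presented as independent evidence. It concerns 18 of 33 scans per subject.

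The software-calculated OCT variables and the impedance half-life are not affected. No figure can be given for how far agreement might be inflated, because the documents give neither the share of unclear scans nor any agreement measure.

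The conclusion assumes that pore closure is judged by eye, that the scans are stored and can be recoded, and that the attachments contain no masking procedure. It is a worthwhile improvement, not a flaw that invalidates the study.

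**What to change.** State in VII.E.6 and XI.1 that:

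1. The 18 scans per subject that could show micropores are mixed with the 15 scans of skin without a micropatch, which serve as negatives. All are given random codes and shuffled across subjects, sites and visits by an existing team member who does not read them.
2. Each scan is called open or closed by one written rule, and any manual OCT measurement is made, before codes, self-identified group or impedance data are linked.
3. The masked calls are then compared with the impedance result in a way fixed beforehand. The calls are binary and the half-life is continuous, so the link must be spelled out. One option is to tabulate same-visit impedance by open or closed call.

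The cost is file renaming and shuffling, with no added subjects, visits or equipment. VII.D.12 lists three team members in the consent process, so splitting coding from reading looks feasible, although the documents do not assign image reading to anyone. There are two downsides. Occlusion or visit may sometimes be guessed from the image, and the reader loses the earlier scan of the same site as a reference for judging closure.

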#### **I.5**

##### ***Specify your research question(s), study aims or hypotheses (do not indicate "see protocol")***

This study aims to visualize micropores and measure micropore closure rates following micropatch application at 3 anatomical sites in subjects from different racial/ethnic groups. Another study aim is to quantify differences in skin structure and blood flow using OCT imaging. We hypothesize that OCT images of micropores in the skin will provide a complementary approach to calculating micropore lifetime, when combined with impedance calculations.

#### **I.6**

##### ***Background and significance and/or Preliminary studies related to this project.***

##### ***(do not indicate "see protocol")***

The skin serves an integral role in protecting the body from harmful environmental stressors. Much of the skin's barrier capabilities can be attributed to the stratum corneum, the outermost layer of the epidermis. Although the stratum corneum is beneficial in protecting against absorption of foreign compounds and excessive loss of water, it is an obstacle for most transdermal drug delivery methods. Transdermal delivery allows a drug to reach the systemic blood supply while avoiding common obstacles such as first pass hepatic metabolism and inconsistent plasma concentrations [1]. Other benefits of transdermal delivery include improved patient compliance, and pain-free delivery [2]. However, few drugs can be transdermally delivered because of strict physicochemical properties required for skin permeation, including molecular weight in Daltons or octanol-water partition coefficient [3]. One way to aid transdermal delivery is through microneedles, which bypass the stratum corneum and increase the list of therapeutics that can be successfully delivered through the skin.

Microneedles are micron-scale projections that form transient micropores in the epidermis. When using solid microneedles, the micropores are created from the initial insertion of the microneedles, but then the microneedles are discarded and do not remain in the skin for any period of time. For this type of microneedle technique, the ability of the micropores to remain open is crucial for effective drug delivery (in a drug delivery study, a medication patch would be applied over the newly-created micropores). There have been some studies quantifying micropore lifetime in human subjects, though the populations studied have been very homogenous and do not represent the full range of skin types that might benefit from microneedle-assisted drug delivery. There has been a lack of studies studying micropore closure kinetics among different racial/ethnic skin types. There is also contradicting evidence that other variables, such as transepidermal water loss (TEWL), skin elasticity, and epidermal and dermal thickness, vary among different skin types as well [4-5]. More research is necessary to better understand this area, and this can be achieved using new imaging methods such as dynamic optical coherence tomography (OCT).

OCT is a noninvasive and nondestructive technique that is already recognized as a powerful medical imaging technique

in the field of ophthalmology, in which it is used for imaging the retina. It is a real time, in-vivo technique that has also been used for skin imaging. The instrument uses an echo technique for image collection that is similar in concept to ultrasound, with the exceptions that OCT uses light waves (instead of sound waves) and provides better resolution. OCT allows for noninvasive observation of the skin in a vertical plane up to a depth of ~1 mm, capturing two and three-dimensional images [6]. This allows for visualization of multiple skin structures such as the epidermis, dermis, epidermal junction, and hair follicles. Dynamic OCT allows for the visualization of the microvasculature, along with the skin structures. Previous studies have successfully utilized OCT to image polymeric microneedles in the skin [7-8]. However, OCT has not been used to visualize the micropores formed from metal microneedles, which is the primary focus of the work in our lab group. To date, there are also no studies using OCT to study the microvasculature differences among different racial/ethnic skin types.

In our research program we recently demonstrated that epidermal barrier restoration is slower after microneedle application in darker skin types [9]. We also demonstrated that the use of tristimulus colorimetry as a quantitative measurement of skin color is a better indicator of skin variability than race self-reported by subjects. Using OCT to visualize the skin structures will provide a visual, complementary confirmation of these findings that will augment the impedance calculations that we use as a surrogate measure to determine how long the micropores remain open.

In the current study we will use dynamic OCT and other noninvasive measurements of epidermal properties to comprehensively examine differences in skin properties and micropore closure timeframes after microneedle application in a population of healthy human subjects with racial/ethnic skin.

